#### 8.10.1 Concomitant Therapy

A concomitant therapy is any non-protocol specified drug or substance (including over-the-counter medications, herbal medications and vitamin supplements) administered between Screening and the end of the post-treatment evaluation period. All concomitant medications/treatments and significant non-drug therapies (including supplements and assistive devices) received by a subject, including changes in the subject's current medications, must be recorded in the subject's source documents and CRF. Subjects taking over the counter (OTC) omega-3 fatty acids should make every effort to remain on the same brand throughout the study.

#### **Allowed Concomitant Therapy**

Ibuprofen may be used for symptomatic pain relief. Any other therapy for pain (including OTC medications such as acetaminophen) should be approved by the Sponsor Medical Monitor or designee.

#### **Disallowed Concomitant Therapy**

The use of prescription and OTC medications including nonsteroidal anti-inflammatory drugs (with the exception of occasional ibuprofen) is prohibited during this study unless the occurrence of an AE requires a drug therapy. In cases when there is no AE, the Investigator must consult the Sponsor Medical Monitor to decide on subject continuation or withdrawal from the study.

The medications and therapy identified in exclusion criteria, Section 5.2 are also disallowed concomitant medications and are prohibited during the course of study, unless there is a safety concern. In those cases the Medical Monitor needs to be notified and rationale provided by the Investigator.

Concomitant therapy with oral corticosteroids used as replacement therapy for pituitary adrenal disease as well as inhaled steroid therapy (e.g., Pulmicort®), or intra-articular, or topical may be acceptable; however, the subject must be on a stable regimen for at least 4 weeks prior to Screening. All exceptions should be discussed with the Sponsor Medical Monitor.

Subject should consult with the Site Investigator or designee prior to initiating any new medication, including non-prescription or herbal compounds or any other non-drug therapy.

#### 8.10.2 Concomitant Procedures

A concomitant procedure is any therapeutic intervention (e.g., surgery/biopsy, physical therapy) or diagnostic assessment (e.g., blood gas measurement, bacterial cultures) performed between Screening and the end of the post-treatment evaluation period.

#### 8.11 Treatment Compliance

Compliance with treatment dosing is to be monitored and recorded by Study Center staff. The Study Center staff is required to document the receipt, dispensing, and return/destruction of study medication. Subjects that are self-administering study medication at home must record treatment in a dosing diary that will be reviewed periodically by Study Center staff and the Clinical Monitor.

#### 9. SERIOUS AND NON-SERIOUS ADVERSE EVENT REPORTING

#### 9.1 Sponsor Review of Safety Information

Safety information will be collected, reviewed, and evaluated by the Sponsor or designee in accordance with the Safety Management Plan throughout the conduct of the clinical trial.

#### 9.2 Regulatory Requirements

The Sponsor or designee is responsible for regulatory submissions and reporting to the Investigators of serious adverse events (SAEs) including suspected unexpected serious adverse reactions (SUSARs) per the International Conference on Harmonization (ICH) guidelines E2A and ICH E6. Country-specific regulatory requirements will be followed in accordance with local country regulations and guidelines. Institutional Review Boards (IRB)/Independent Ethics Committees (IEC) will be notified of any SAE according to applicable regulations. In addition to the Investigator's assessment of relatedness, the Sponsor or designee will evaluate the available information and perform an independent assessment of

relatedness. While the Sponsor may upgrade an Investigator's decision it is not permissible to downgrade the Investigator's opinion for the purposes of determining whether the SAE meets the definition of a SUSAR. For the purpose of regulatory reporting of SUSARs, there are no "expected" AEs in this study population.

## 9.3 Definitions

#### 9.3.1 Adverse Event

An adverse event is any unfavorable and unintended sign (including a clinically-significant abnormal laboratory finding, for example), symptom, or disease temporally associated with the Study or use of investigational drug product, whether or not the AE is considered related to the investigational drug product.

#### 9.3.2 Adverse Reaction and Suspected Adverse Reaction

An adverse reaction is any AE caused by the Study Drug. A suspected adverse reaction is any AE for which there is a reasonable possibility that the drug caused the adverse event. A suspected adverse reaction implies a lesser degree of certainty about causality than an adverse reaction.

#### 9.3.3 Serious Adverse Event (SAE)

A serious adverse event is any adverse event that in the view of either the Investigator or Sponsor, meets any of the following criteria:

- Results in death
- Is life threatening: that is, poses an immediate risk of death at the time of the event

An AE or suspected adverse reaction is considered "life-threatening" if, in the view of either the Investigator or Sponsor, its occurrence places the subject at immediate risk of death. It does not include an AE or suspected adverse reaction that, had it occurred in a more severe form, might have caused death

• Requires inpatient hospitalization or prolongation of existing hospitalization

Hospitalization is defined as an admission of greater than 24 hours to a medical facility and does not always qualify as an AE

- Results in a persistent or significant incapacity or substantial disruption of the ability to conduct normal life functions
- Results in a congenital anomaly or birth defect in the offspring of the subject (whether the subject is male or female)
- Important medical events that may not result in death, are not life-threatening, or do not require hospitalization may also be considered serious when, based upon appropriate medical judgment, they may jeopardize the subject and may require medical or surgical intervention to prevent one of the outcomes listed in this definition. Examples of such medical events include allergic bronchospasm requiring intensive treatment in an emergency room or at home, blood dyscrasias or convulsions that do not result in inpatient hospitalization, or the development of drug dependency or drug abuse.

# 9.3.3.1 Adverse Events of Special Interest

For the purpose of this study severe reductions in platelet count  $< 50,000 \text{ mm}^3$  are considered as an AE of special interest and should be subject to expediting reporting to the Sponsor following the same requirements as for SAE reporting (Section 9.4.1).

## 9.4 Monitoring and Recording Adverse Events

Any pre-existing conditions or signs and/or symptoms present in a subject prior to the start of the Study (i.e., before informed consent) should be recorded as Medical History and not recorded as AEs unless the pre-existing condition worsened. The Investigator should always group signs and symptoms into a single term that constitutes a **single unifying diagnosis** if possible.

#### 9.4.1 Serious Adverse Events

In the interest of subject safety, and in order to fulfill regulatory requirements, all SAEs (regardless of their relationship to Study Drug) should be reported to the Sponsor or designee within 24 hours of the Study Center's first knowledge of the event. The collection of SAEs will begin after the subject signs the informed consent form and stop at the end of the subject's follow-up period. An Initial Serious Adverse Event Form should be completed and a copy should be faxed to the Sponsor or designee.

The contact information for reporting SAEs is as follows:

Attention: INC Research, LLC

Email:[contact]

[contact]

Detailed information should be actively sought and included on Follow-Up Serious Adverse Event Forms as soon as additional information becomes available. All SAEs will be followed until resolution. SAEs that remain ongoing past the subject's last protocol-specified follow-up visit will be evaluated by the Investigator and Sponsor. If the Investigator and Sponsor agree the subject's condition is unlikely to resolve, the Investigator and Sponsor will determine the follow-up requirement.

#### 9.4.2 Non-Serious Adverse Events

The recording of non-serious AEs will begin after the subject signs the informed consent form and will stop at the end of the subject's follow-up period. The Investigator will monitor each subject closely and record all observed or volunteered AEs on the Adverse Event Case Report Form.

#### 9.4.3 Evaluation of Adverse Events (Serious and Non-Serious)

The Investigator's opinion of the following should be documented on the Adverse Event Case Report Form:

# 9.4.3.1 Relationship to the Study Drug

The event's relationship to the Study Drug (ISIS 703802) is characterized by 1 of the following:

- **Related:** There is clear evidence that the event is related to the use of Study Drug, e.g., confirmation by positive re-challenge test
- **Possible:** The event cannot be explained by the subject's medical condition, concomitant therapy, or other causes, and there is a plausible temporal relationship between the event and Study Drug (ISIS 703802) administration
- Unlikely/Remote: An event for which an alternative explanation is more likely (e.g., concomitant medications or ongoing medical conditions) or the temporal relationship to Study Drug (ISIS 703802) administration and/or exposure suggests that a causal relationship is unlikely (For reporting purposes, Unlikely/Remote will be grouped together with Not Related)
- Not Related: The event can be readily explained by the subject's underlying medical condition, concomitant therapy, or other causes, and therefore, the Investigator believes no relationship exists between the event and Study Drug

#### 9.4.3.2 Severity

The severity of AEs and SAEs will be graded based on criteria from the Common Terminology Criteria for Adverse Events (CTCAE) Version 4.03, June 2010 (refer to Appendix D). Any AE not listed in Appendix D will be graded as follows:

- Mild: The event is easily tolerated by the subject and does not affect the subject's usual daily activities
- **Moderate:** The event causes the subject more discomfort and interrupts the subject's usual daily activities
- Severe: The event is incapacitating and causes considerable interference with the subject's usual daily activities

If the event is an SAE, then all applicable seriousness criteria must be indicated (criteria listed in Section 9.3.3).

#### 9.4.3.3 Action Taken with Study Drug

Action taken with Study Drug (ISIS 703802) due to the event is characterized by 1 of the following:

- None: No changes were made to Study Drug (ISIS 703802) administration and dose
- **Permanently Discontinued:** Study drug was discontinued and not restarted
- **Temporarily Interrupted, Restarted Same Dose:** Dosing was temporarily interrupted or delayed due to the AE and restarted at the same dose
- **Temporarily Interrupted, Restarted Reduced Dose:** Dosing was temporarily interrupted or delayed due to the AE and restarted at the next lower dose

# 9.4.3.4 Treatment Given for Adverse Event

Any treatment (e.g., medications or procedures) given for the AE should be recorded on the Adverse Event Case Report Form. Treatment should also be recorded on the concomitant treatment or ancillary procedures eCRF, as appropriate.

## 9.4.3.5 Outcome of the Adverse Event

If the event is a non-serious AE, then the event's outcome is characterized by 1 of the following: **AE Persists:** Subject terminates from the trial and the AE continues:

- **Recovered:** Subject recovered completely from the AE
- **Became Serious:** The event became serious (the date that the event became serious should be recorded as the Resolution Date of that AE and the Onset Date of the corresponding SAE)
- Change in Severity (if applicable): AE severity changed

If the event is an SAE, then the event's outcome is characterized by 1 of the following: **Ongoing:** SAE continuing:

- **Persists (as non-serious AE):** Subject has not fully recovered but the event no longer meets serious criteria and should be captured as an AE on the non-serious AE eCRF (the SAE resolution date should be entered as the date of onset of that AE)
- **Recovered:** Subject recovered completely from the SAE (the date of recovery should be entered as the SAE resolution date)
- **Fatal:** Subject died (the date of death should be entered as the SAE resolution date)

#### 9.5 **Procedures for Handling Special Situations**

#### 9.5.1 Abnormalities of Laboratory Tests

Clinically-significant abnormal laboratory test results may, in the opinion of the Investigator, constitute or be associated with an AE. Examples of these include abnormal laboratory results that are associated with symptoms, or require treatment (e.g., bleeding due to thrombocytopenia, tetany due to hypocalcemia, or cardiac arrhythmias due to hyperkalemia). Whenever possible, the underlying diagnosis should be listed in preference to abnormal laboratory values as AEs. Clinically-significant abnormalities will be monitored by the Investigator until the parameter returns to its baseline value or until agreement is reached between the Investigator and Sponsor Medical Monitor. Laboratory abnormalities deemed not clinically-significant (NCS) by the Investigator should not be reported as AEs. Similarly, laboratory abnormalities reported as AEs by the Investigator should not be deemed NCS on the laboratory sheet. The Investigator is responsible for reviewing and signing all laboratory reports. The signed clinical laboratory reports will serve as source documents and should include the Investigator's assessment of clinical significance of out of range/abnormal laboratory values. All platelet count results must be reviewed promptly (within 48 hours of receipt) by the Investigator or the designee to ensure that the count has not met the stopping rule and to determine whether the rate of decline is suggestive that the patient could be approaching the dose interruption rule of 75,000/mm^3 as specified in Section 8.6.3. Any case of a platelet count reduction to levels below 50,000/mm^3 (Grade 3 or Grade 4) is considered an adverse event of

special interest and should be reported in an expedited fashion to the Sponsor as per Sections 9.3.3.1 and 9.4.1).

All results of liver function tests must be reviewed promptly (within 48 hours of receipt) by the Investigator or the designee to ensure that the result has not met the stopping rules per Section 8.6.1.

All results of renal function tests must be reviewed promptly (within 48 hours of receipt) by the Investigator or the designee to ensure that the result has not met the stopping rules per Section 8.6.2.

# 9.5.2 Prescheduled or Elective Procedures or Routinely Scheduled Treatments

A prescheduled or elective procedure or a routinely scheduled treatment will not be considered an SAE, even if the subject is hospitalized; the Study Center must document all of the following:

- The prescheduled or elective procedure or routinely scheduled treatment was scheduled (or was on a waiting list to be scheduled) prior to obtaining the subject's consent to participate in the Study
- The condition that required the prescheduled or elective procedure or routinely scheduled treatment was present before and did not worsen or progress in the opinion of the Investigator between the subject's consent to participate in the Study and the timing of the procedure or treatment
- The prescheduled or elective procedure or routinely scheduled treatment is the sole reason for the intervention or hospital admission

# 9.5.3 Dosing Errors

Study Drug (ISIS 703802) errors should be documented as Protocol Deviations. A brief description should be provided in the deviation, including whether the subject was symptomatic (list symptoms) or asymptomatic, and the event accidental or intentional. Dosing details should be captured on the Dosing eCRF. If the subject takes a dose of Study Drug that exceeds protocol specifications and the subject is symptomatic, then the symptom(s) should be documented as an AE and be reported per Section 9.4. **Should an overdose occur**, the Investigator or designee should refer to the Guidance to Investigator's section of the Investigator's Brochure and contact the Sponsor or designee within 24 hours.

#### 9.5.4 Contraception and Pregnancy

Subjects must continue to use appropriate contraception with their partners, or refrain from sexual activity, as described in Section 6.3.1. If a subject becomes pregnant or a pregnancy is suspected, or if a male subject makes or believes that he has made someone pregnant during the Study, then the Study Center staff must be informed immediately. An Initial Pregnancy Form should be submitted to the Sponsor or designee within 24 hours of first learning of the occurrence of pregnancy. Follow-up information including delivery or termination is reported by designating as 'Follow-up' on the Pregnancy Forms and reported within 24 hours. Payment for all aspects of obstetrical care, child or related care will be the subject's responsibility. Female subjects: If a suspected pregnancy occurs while on the Study (including follow-up), a pregnancy test will be performed. The subject with a confirmed pregnancy will be immediately withdrawn from treatment with Study Drug. However, the subject will be encouraged to complete the post-treatment follow-up portion of the Study to the extent that study procedures do not interfere with the pregnancy. Regardless of continued study participation, the study physician will assist the subject in getting obstetrical care and the progress of the pregnancy will be followed until the outcome

of the pregnancy is known (i.e., delivery, elective termination, or spontaneous abortion). If the pregnancy results in the birth of a child, the Study Center and Sponsor may require access to the mother and infant's medical records for an additional 8 weeks after birth. Follow-up will be performed to the extent permitted by the applicable regulations and privacy considerations. Male subjects: The progress of the pregnancy of a male subject's partner should be followed until the outcome of the pregnancy is known (i.e., delivery, elective termination, or spontaneous abortion). If the pregnancy results in the birth of a child, the Study Center and Sponsor may request access to the mother and infant's medical records for an additional 8 weeks after birth. Follow-up will be performed to the extent permitted by the applicable regulations and privacy considerations.

#### **10. STATISTICAL CONSIDERATIONS**

#### 10.1 Study Endpoints, Subsets, and Covariates

#### 10.1.1 Primary Endpoint

• The effect of ISIS 703802 on the percent change from Baseline in fasting triglyceride levels (TG) at week 27

#### 10.1.2 Secondary Endpoints

- Change from Baseline in AUC plasma glucose, serum insulin, serum C-peptide, free fatty acid, serum ghrelin, GIP, GLP-1, and PYY and incretin hormones in response to a mixed meal test (MMT)
- Change from Baseline in lipids and lipoproteins including high-density lipoprotein cholesterol (HDL-C), low-density lipoprotein cholesterol (LDL-C), total cholesterol (TC), very low-density lipoprotein cholesterol (VLDL-C), non-HDL-C, apolipoprotein B (apoB), apolipoprotein B-48 (apoB-48), apolipoprotein B-100 (apoB-100), apolipoprotein A-1 (apoA-1), apolipoprotein C-III (apoC-III :total, chylomicron, VLDL, LDL and HDL), Lipoprotein a [Lp(a)], free fatty acids (FFA), and glycerol levels, lipoprotein particle size/number
- Change from Baseline in glycosylated hemoglobin (HbA1c)
- Change from Baseline in homeostasis model assessment-estimated insulin resistance (HOMA-IR)
- Change from Baseline in adiponectin and leptin
- Change from Baseline in hepatic fat fraction (as assessed by magnetic resonance imaging [MRI])
- Changes from Baseline in body fat distribution for various areas in the body as measured by skinfold thickness and DEXA; VAT and SAT as measured by MRI; body weight, waist circumference and waist/hip ratio
- Change from Baseline in quality of life and pain score

#### **10.2** Sample Size Considerations

There is no statistical rationale for the selected sample size. The sample size is selected based upon prior experience with ISIS 703802 to ensure that the safety, tolerability and efficacy of ISIS 703802 can be explored in an ultra-rare condition before enrolling subjects in a larger study.

#### 10.3 **Populations**

Safety Set: All subjects who are enrolled and receive at least 1 dose of Study Drug. PK Set: All subjects who receive at least 1 dose of Study Drug and have at least 1 evaluable PK sample.

# **10.4 Definition of Baseline**

For fasting lipid measurements, the Baseline is defined as the average of Day 1 pre-dose assessment and the last measurement prior to Day 1.

For other measurements, Baseline will be the last non-missing assessment prior to the first dose of Study Drug.

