#### 8.6 Stopping Rules

For the purposes of stopping rules, Baseline is defined as the average of Day 1 pre-dose assessment and the last measurement prior to Day 1.

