# 10.6.5 Pharmacodynamic Analysis

The following parameters will be measured throughout the trial and change at week 27 relative to Baseline will be summarized:

- ANGPTL3
- HDL-C
- LDL-C
- TC
- VLDL-C
- non-HDL-C
- apoB
- apoB-48
- apoB-100
- apoA-1
- apoC-III
- Lp(a)
- FFA
- Glycerol levels
- Lipoprotein particle size/number

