# Subjects on stable diet known to the investigator and followed at the site may go from Screening to qualification without the diet run-in period.

† Qual =Qualification

ISIS 703802-CS5

All procedures and study samples are to be done pre-dose at respective visits, unless specified

- a Full physical exam will be performed at the screening visit and an abbreviated physical exam will be performed during treatment and follow-up periods.
- b Height only required at Screening
- c Mixed Meal Test-refer to Appendix E for further details
- d MRI and DEXA scan will only be performed during Screening after all other eligibility criteria are met. MRI should be performed 10 days (+/- 2 days) prior to anticipated Day 1 date to allow time for result reporting and analysis. DEXA scan should be performed as close to anticipated Day 1 date as possible.
- e All tests listed in Appendix B under Extended Urinalysis should be performed, including routine urinalysis, urine microscopy, UACR and UPCR.
- f Assessments and procedures to be conducted by either a home healthcare service or the Study Center. Subject Study Center visits must be no more than 4 weeks apart during the treatment period.
- g Urine samples for renal biomarkers will be collected. Sample analysis will be conducted in accordance with Safety Monitoring for Renal Function (Section 8.5.2).
- h During follow-up period, hematology sampling for platelet values are taken every 14 days (+/- 2 days) for 6 weeks after last dose of Study Drug, then at Week 8 and Week 13 Follow-up visits.
- i Serum Creatinine and Cys-C will be collected as a part of chemistry panel at visits when chemistry panel is performed, or as stand-alone samples at time points when a chemistry panel is not performed.
- j Blood samples to be collected after an overnight fast of at least 10 hours and preferably not more than 12 hours, unless tests are repeated for safety reasons.
- k If the platelet value, serum creatinine or liver enzyme tests are uninterpretable (e.g., due to clumping, hemolysis or quantity not sufficient) a repeat blood specimen should be re-drawn as soon as possible (ideally within 7 days). All platelet count results will be reviewed promptly (within 48 hours of receipt) by the Investigator as per Section 6.2.1. Any case of a platelet count ≤ 50,000/mm^3 should be reported in an expedited fashion to the Sponsor.
- Refer to Appendix C for PK Sampling schedule.

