PD Panel         • ANGPTL3         • Insulin         • Proinsulin         • C-peptide         • Fructosamine         • Glycated albumin         • Delipidated Free Glycerol         • Fasting Plasma Glucose         Coagulation         • aPTT (sec)	
 
ApoB
 
ApoB-48
 
ApoB-100
 
Apo A-1
 
ApoCIII (total, chylomicron, LDL, HDL, VLDL)
 
Delipidated Free Glycerol
 
Ceramides
 
Sphingolipids
 
Diacyglycerol
 
	
 
Inflammatory
 
hs-CRP
 
IL-6
 
IFN gamma
 
TNF alpha
 
Leptin
 
Adiponectin
 
 Genetic Testing 
 
Genetic sequencing of FPL causing genes
 
	
 
C-peptide
 
Insulin
 
Serum ghrelin
 
GIP
 
GLP-1
 
PYY
 
Incretin hormones
 

-			

1 Plasma PK samples may also be used for profiling of drug binding proteins, bioanalytical method validation purposes, stability assessments, metabolite assessments, or to assess other actions of ISIS 703802 with plasma constituents

2 All samples will be collected, handled and stored under the conditions specified for the assays. Please refer to the study Laboratory Manual for details on the appropriate handling and storage methods for biomarker and other samples.

3 Blood will be collected to assess genetic evidence of FPL (e.g., mutations in LMNA, PPAR-γ, AKT2, CIDEC, PLIN1 genes). May not be collected if adequate genetic data are available in medical history or if patient does not consent to genetic testing

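### Section 10.4 averages two pre-dose visits for fasting lipids but takes a single value for ANGPTL3 and the rest of the fasting PD Panel drawn at the same visits; extending the lipid rule would give a modest precision gain at no sampling cost

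*Combined protocol and SAP*

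**What the plan says.** Section 10.4 of Protocol Amendment 1 has two baseline rules. For lipids: "For fasting lipid measurements, the Baseline is defined as the average of Day 1 pre-dose assessment and the last measurement prior to Day 1". For the rest: "For other measurements, Baseline will be the last non-missing assessment prior to the first dose of Study Drug".

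Sections 8.5 and 8.6 also use two values. For stopping, "For the purposes of stopping rules, Baseline is defined as the average of Day 1 pre-dose assessment and the last measurement prior to Day 1"; Section 8.5 has an equivalent rule for safety monitoring.

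The Appendix A schedule marks both the PD Panel and the Extended Lipid Panel at Screening, Qualification and Day 1. Both carry the same fasting footnote, "Blood samples to be collected after an overnight fast of at least 10 hours and preferably not more than 12 hours", and a general note adds "All procedures and study samples are to be done pre-dose at respective visits, unless specified". Appendix B lists ANGPTL3, insulin, C-peptide and "Fasting Plasma Glucose" under the PD Panel. It lists delipidated free glycerol under both panels.

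On use, Section 10.6.5 states "The following parameters will be measured throughout the trial and change at week 27 relative to" Baseline is to be summarised, and ANGPTL3 heads its list. Change in HOMA-IR is a secondary endpoint in Section 10.1.2 and is summarised at Week 27 under Section 10.6.3. Section 3.3 plans about 3 subjects, possibly 6. Section 10.2 gives no statistical rationale for that number.

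**The concern.** Two panels share the same pre-dose visits and the same fasting condition but get different baseline rules, and no reason is given. ANGPTL3, the drug's target, is judged from one pre-dose value per subject, while the lipid changes that will be read beside it rest on two. With about 3 subjects, one unusual Day 1 value can shift the mean change noticeably. The Qualification value that would dampen it has already been collected but does not enter Baseline.

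What is at stake is the precision of a pharmacodynamic summary and, under a condition discussed below, of one secondary endpoint.

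**Working it through.** **Which rule applies.** ANGPTL3 is a protein on the PD Panel, not a lipid, so the single-value rule governs it. When the Day 1 pre-dose draw is present, it is the last non-missing value. The last draw before it on the schedule is Qualification.

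**No figure to reproduce.** The protocol states no SD, power or precision target. Everything below is relative and rests on assumed variances.

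**Model.** On the log scale (to first order, also for percent change), let σ² be the within-subject variance per draw, τ² the between-subject variance of true response, m the number of baseline draws averaged, and ρ the correlation between baseline errors. Follow-up error is taken as independent of baseline error.

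- Independent errors: Var(change) = τ² + σ²(1 + 1/m)
- Correlated baseline errors, τ² = 0: Var(change) = σ²[1 + (1 + (m − 1)ρ)/m]

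**One draw (m = 1) against two (m = 2, Qualification and Day 1).**

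| Assumption | Variance ratio, m = 2 to m = 1 | SD ratio | Reduction in SD |
|---|---|---|---|
| τ² = 0, ρ = 0 | 1.5/2 | 0.866 | 13.4% |
| τ² = σ², ρ = 0 | 2.5/3 | 0.913 | 8.7% |
| τ² = 4σ², ρ = 0 | 5.5/6 | 0.957 | 4.3% |
| τ² = 0, ρ = 0.3 | 1.65/2 | 0.908 | 9.2% |
| τ² = 0, ρ = 0.5 | 1.75/2 | 0.935 | 6.5% |
| τ² = 0, ρ = 0.7 | 1.85/2 | 0.962 | 3.8% |

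The first row is the ceiling. There, 3 subjects carry the information of 3 × 2/1.5 = 4.0. In the second and third rows they carry that of 3.6 and 3.27.

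**In absolute terms, for an assumed within-subject CV of 20% to 40%.** With σ = √ln(1 + CV²), σ is 0.198 to 0.385. At the ceiling, the SD of one subject's log change falls from about 0.28 to 0.24 at the low end, and from about 0.54 to 0.47 at the high end.

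**Against the expected effect.** Section 2.3.4 reports Phase 1 ANGPTL3 reductions of 46.6% to 84.5%. On the log scale these are −ln(0.534) = 0.63 and −ln(0.155) = 1.86.

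**Scale.** Section 10.6.5 says only that change is summarised. For absolute change with multiplicative error, the error SD scales with √[(1 − r)² + 1/m]. At the Phase 1 reductions the cut would be 21.8% to 28.5% with no response heterogeneity. Absolute change also varies with each subject's true starting level, which averaging does not reduce, so I do not rely on that range.

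**The case against.** The strongest reply is that nothing here is an error. The last value before dosing is an unambiguous, pre-specified and conventional baseline, and it introduces no bias. That stands: the point is an improvement, not a correction.

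It can also be said that the gain hardly matters for ANGPTL3. If its CV were near 20%, a move in SD from 0.28 to 0.24 would rarely change the reading of an effect of 0.63 to 1.86. The protocol plans descriptive summaries, puts all laboratory data in listings (Section 10.6) and allows further analyses (Section 10.6.6). That also stands, and it limits the importance of the point.

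Four stronger readings are tempting, and the documents do not support them.

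- **Averaging all three pre-dose draws, for an 18% gain.** The arithmetic is √[(4/3)/2] = 0.816. However, under Section 6.1.1 subjects not on a stable diet have a 4-week diet run-in after Screening, so for them Screening and Day 1 are not exchangeable.
- **Treating 13% as the expected gain.** It requires identical true responses and independent errors. The planned SD and SE across subjects also contain response differences.
- **Taking the HOMA-IR baseline to be the Day 1 value.** No section says which samples feed HOMA-IR. The mixed meal test also draws fasting glucose and insulin, at Qualification, Week 13 and Week 27 (Appendices A and E). If HOMA-IR comes from that test, its only baseline is Qualification and there is no like-for-like second draw.
- **Taking averaging to be free of selection because neither marker is an entry criterion.** Inclusion criterion 5 selects on triglycerides at Screening and Qualification. If glucose or insulin moves with triglycerides, the Qualification value could bring slight regression to the mean into HOMA-IR. Day 1 is not a triglyceride selection visit.

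The age of the Qualification draw is also unsettled. Appendix A gives Day −7 to −1, while Sections 3.4 and 3.4.1 allow up to 2 weeks. Appendix A footnote d puts the MRI 10 ± 2 days before Day 1, after all other eligibility is met, which implies Qualification at least 8 days before dosing. None of this defeats the ANGPTL3 case, because the lipid rule already accepts the same earlier draw.

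**Conclusion.** The point holds as a minor improvement. Section 10.4 leaves a scheduled, comparable fasting ANGPTL3 draw out of Baseline while averaging those same two visits for lipids. Using it would lower the SD of log change by at most 13%, and by about 4% to 9% under moderate response heterogeneity (τ² of one to four times σ²) or correlation between draws (0.3 to 0.7). These variances are assumptions, and the documents supply none.

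For HOMA-IR and its components the point is conditional on their being calculated from PD Panel samples throughout. The primary triglyceride endpoint already has a two-value baseline and is untouched. Even with the change, 3 subjects remain very few: a 95% t-interval would have a half-width of 4.303/√3 = 2.48 SDs.

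**What to change.** In Section 10.4, extend the lipid rule to the fasting PD Panel:

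- **ANGPTL3:** Baseline is the average of the Day 1 pre-dose value and the last value before Day 1 (Qualification), or Day 1 alone if the earlier value is missing.
- **Fasting glucose, insulin, C-peptide and HOMA-IR:** use the same rule only if these are taken from PD Panel samples at every visit, not from mixed meal test samples. State that source explicitly. Compute HOMA-IR at each draw, then average.
- **Screening:** leave this draw out.

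The cost is a few sentences, with no new samples or visits. There are two small downsides. The Qualification draw may be up to about 2 weeks old at dosing, and the timing in Appendix A and Sections 3.4 and 3.4.1 should be reconciled in the same edit. HOMA-IR may also pick up slight regression to the mean, which listing the Day 1-only change beside the averaged one would make visible.
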